#### 10.1.2 Severity of adverse events

- Mild: Not influence daily activities;
- Moderate: Influence daily activities;
- Severe: Lose the ability of daily activities.

#### 10.1.3 Relationship between adverse events and the investigational product or surgery

The investigator assesses the relationship between adverse events and the investigational product or surgery according to the following criteria:

- (1) Relationship to the investigational medical device:
  - Certainly related: The reaction is a known reaction type of the suspected product;
  - Possibly related: The reaction is a known reaction type of the suspected product; but this reaction may

also be caused by clinical conditions of the patient or other treatment methods;

- Unlikely related: The reaction is not a known reaction type of the suspected product; this reaction may be caused by clinical conditions of the patient or other treatment methods;
- Unrelated: The reaction is not a known reaction type of the suspected product; this reaction may be caused by clinical conditions of the patient or other treatment methods; The reaction disappears when the condition improves or other treatment methods cease. The reaction appears again when other treatment methods are reused;
- Undeterminable: The reaction is similar to a known reaction type of the suspected product;

  Meanwhile, the same reaction may be caused by other treatment methods.

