#### 11.3.4 Safety evaluation

The statistical description will be performed for the condition of each complication. A table will be made to describe the type, severity, frequency and relationship to the investigational medical device of the AE. The incidence rate of AE will be calculated. Study discontinuation due to AEs as well as severe or serious AEs

will be specially described. The statistical description will be performed for the working condition of the system.

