#### 13.3 Review and Approval of the Protocol

This trial protocol must be approved by the medical ethics committee. The clinical study report will be submitted to CFDA for the registration of the investigational medical device.

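### The causality scale in Protocol 10.1.3 bars any reaction of a type not already known from a related grade, leaves one case with no grade, and has overlapping grades

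*Protocol*

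**What the plan says.** Protocol section 10.1.3 (1) defines five grades for the relationship to the device:

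- The top grade has one condition: "Certainly related: The reaction is a known reaction type of the suspected product".
- The second keeps that condition and adds that the patient's condition or another treatment might also be the cause: "Possibly related: The reaction is a known reaction type of the suspected product".
- The third reverses the first condition and again names another possible cause: "Unlikely related: The reaction is not a known reaction type of the suspected product".
- The fourth starts the same way, "Unrelated: The reaction is not a known reaction type of the suspected product", and repeats the other possible cause. It then adds a course that tracks that cause, "The reaction disappears when the condition improves or other treatment methods cease", with return of the reaction on re-exposure to the other treatment.
- The fifth reads "Undeterminable: The reaction is similar to a known reaction type of the suspected product", with another treatment as a possible cause.

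Section 10.1.3 (2) repeats the structure for the relationship to surgery. Section 11.3.4 uses the rating: its adverse event table is to show type, severity, frequency and "relationship to the investigational medical device of the AE". Section 13.3 says where the report goes: "The clinical study report will be submitted to CFDA for the registration of the investigational medical device".

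**The concern.** A causality scale should let the assessor record that a device probably caused an event even when nobody has seen that event before. Here, prior knowledge of the reaction type is the entry condition for any related grade. That fits poorly with section 7.7, where training is meant to help investigators pick up new information about the product. It also fits poorly with section 1, which calls the device recently developed and its safety relative to hookwire unclear.

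The overlap is a second problem. Section 8.4 places surgery directly after localization, so another treatment is a plausible alternative cause for many events. If one event satisfies two or three definitions, the recorded grade depends on the assessor's habit. What is at stake is whether the relationship column in a report written for device registration can be interpreted.

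**Working it through.** No arithmetic applies, and the protocol gives no figure to reproduce. The check sets the five definitions against the criteria they use.

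Notation, all from section 10.1.3 (1):

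- K: the reaction is of a known type.
- S: it is similar to a known type.
- A: the patient's condition or another treatment could be the cause.
- D: it subsides with the other cause and returns when the other treatment is reused.

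| Grade | Conditions as written |
|---|---|
| Certainly | K |
| Possibly | K and A |
| Unlikely | not K, and A |
| Unrelated | not K, and A, and D |
| Undeterminable | S, and A (other treatment only) |

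Each kind of event is then run through the table:

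| Event | Grades it meets |
|---|---|
| Known type, no other cause | Certainly |
| Known type, another possible cause | Certainly and Possibly; arguably Undeterminable too if the other cause is a treatment |
| New type, another possible cause, no D | Unlikely; also Undeterminable if it resembles a known type and another treatment could explain it |
| New type, another possible cause, with D | Unlikely and Unrelated; also Undeterminable on the same condition |
| New type, no other cause | None |

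Three results follow.

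1. **Barred from a related grade.** K appears in both *Certainly* and *Possibly*. No new reaction type can reach either, whatever its timing or mechanism.
2. **No grade at all.** *Unlikely*, *Unrelated* and *Undeterminable* each presuppose another possible cause. A new reaction with no other explanation, which is the clearest new device signal, has no valid code.
3. **Overlap.** *Certainly* does not exclude other causes, so everything that meets K and A also meets K. *Unrelated* is *Unlikely* with one more condition, so everything in the former meets the latter. *Possibly* and *Undeterminable* differ only in whether the reaction is, or merely resembles, a known type, and in whether the patient's condition counts as an alternative. An assessor will find that line hard to draw.

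The surgery scale in 10.1.3 (2) has the same structure and gives the same results.

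**The case against.** The case on the other side is that this is loose CRF wording with safeguards around it. Much of that stands. Section 10.1.1 requires every adverse event to be recorded. Section 11.3.4 tabulates type, severity and frequency and calculates incidence. Section 10.2.2 has serious events handled and reported whatever their relationship. Section 13.1 sends serious or unexpected events that may affect safety to the ethics committee. The complication endpoints in section 7.1 are counted without the rating.

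For these reasons several stronger readings that a reader might infer are not supported:

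- *That relationship is judged solely on whether the type is known.* Four of the five grades also use another possible cause, and *Unrelated* adds resolution and recurrence.
- *That every new reaction is forced into the two lowest grades.* With no other cause it meets neither, and some new reactions can go to *Undeterminable*.
- *That the table would hide an unexpected event.* The event would still appear by type and count; only its relationship entry would be wrong or blank.
- *That 'Possibly' and 'Undeterminable' are the same category.* On paper they differ, since one requires identity with a known type and the other similarity.
- *That the device has only a short list of known reactions.* The protocol gives no closed list. Section 6.2 names the main puncture complications only, and section 1 cites an earlier multi-center trial of the device.

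It is also fair to say that timing is not wholly absent, because section 10.1.1 counts only events after receipt of the device. But that defines what an adverse event is and does not help to grade one.

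None of this removes the gate on the two related grades, the case with no grade, or the overlap.

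**Conclusion.** The point holds as a minor defect of definition. If the grades are applied as written, all reactions of a type not already known are excluded from *Certainly* and *Possibly*, those with no other cause cannot be graded, and known-type events with another possible cause meet at least two grades. How many events this touches cannot be derived, because the protocol gives no expected frequency of new reaction types.

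The effect stops at the relationship column of a descriptive table. The primary endpoint, the sample size, the rates of pneumothorax, hemorrhage and pleural reaction, adverse event counts and expedited reporting are untouched. The conclusion assumes that assessors follow the stated definitions. An assessor using ordinary judgment might grade a new event sensibly, but only by departing from the protocol.

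**What to change.** Redefine the five grades in 10.1.3 (1) and (2) so that they are mutually exclusive and cover every case. Base them on timing relative to the procedure, plausibility for the device or for surgery, and presence or absence of another sufficient cause. Specifically:

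- Do not require a known reaction type for either related grade.
- State in *Certainly* that other causes have been excluded, which separates it from *Possibly*.
- Separate *Unlikely* from *Unrelated* so that no event meets both.
- Reserve *Undeterminable* for cases with too little information to judge.

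The cost is protocol and CRF wording. A few more adverse events may be labelled related. Nothing changes in the sample size, the endpoints or the tests.

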#### (2) Relationship to surgery:

- Certainly related: The reaction is a known reaction type of the surgery;
- Possibly related: The reaction is a known reaction type of the surgery; but this reaction may also be caused by clinical conditions of the patient or other treatment methods;
- Unlikely related: The reaction is not a known reaction type of the surgery; but this reaction may also be caused by clinical conditions of the patient or other treatment methods;
- Unrelated: The reaction is not a known reaction type of the surgery; this reaction may be caused by clinical conditions of the patient or other treatment methods; The reaction disappears when the condition improves or other treatment methods cease. The reaction appears again when other treatment methods are reused;
- Undeterminable: The reaction is similar to a known reaction type of the surgery; Meanwhile, the same reaction may be caused by other treatment methods.

#### 10.2 Serious Adverse Events

#### 10.2.1 Definition of serious adverse events

A SAE is defined as any adverse event occurred during the clinical trial that results in death, is life-threatening, requires inpatient hospitalization or causes prolongation of existing hospitalization, results in disability/incapacity, influences working competence, and may have caused a congenital anomaly, etc. Although the outcome is not death, life-threatening or hospitalization, some medical events shall also be considered as SAEs if appropriate medical judgment indicates that they may do harm to the subject or require drugs or surgery to avoid the above-mentioned conditions.

#### 10.2.2 Handling and reporting of serious adverse events

In case of any SAE in the trial, regardless of its relationship to the investigational medical device, the investigator shall immediately adopt appropriate treatment and cure measures to the subject and record it in the CRF. Meanwhile, the investigator shall assist the sponsor in reporting the SAE to the PI of the driver unit, the ethics committee, the medical device supervision division of national/local food and drug administration, and the local competent administrative department for health if necessary, within 24 hours after having learned of the SAE. The investigator must carefully fill in the SAE report form item by item, sign and date on the report.

# 11 STATISTICAL METHODS

#### 11.1 Statistical Analysis Population

Full Analysis Set (FAS): Refer to the ideal subject set which is as close as possible to the intention-to-treat (ITT) principle. This dataset is obtained through rejecting the least subject from all enrolled subjects using a reasonable method.

Per-Protocol Set (PPS): also known as effective cases, effective samples and evaluable cases. Per-Protocol Set is a subset of subjects in the FAS whose compliance with the protocol is tight enough. The subjects are considered as compliant if they have received treatment, have measurements of primary indexes, and have no major protocol violation, etc.

Safety Analysis Set (SAS): The subject set used for safety and tolerance evaluation. The SAS shall include all subjects who have used this investigational medical device and have at least one safety record.

Here, we will use the FAS to analysis baseline information, and the primary endpoint and secondary endpoint will use the SAS to analysis.

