### 11.2 Justification for Cases

The null hypothesis: the Successful localization probability of the novel localization device isn't higher compared with hookwire.

The alternative hypothesis: the Successful localization probability of the novel localization is higher compared with hookwire.

 $\alpha$  refers to type I error, while  $\beta$  refers to type II error. Here we consider  $\alpha$  as 0.05, and power(1- $\beta$ ) as 80%. According to some reference and our previous study, we consider the Successful localization probability of hookwire as 89% and the Successful localization probability of the novel localization device as 97%, with

one side and the ratio of 2 between control group and intervention group.

We use PASS 11 with Fisher's exact test to calculate the sample size, getting control group with 116 and intervention group with 232. Taking possible 15% drop-out into account, every group will be enrolled 136 patients in the control group and 273 in the intervention group at least. Here, if we can enroll more patients during enrollment time, the patients could be included in our study. This clinical trial can be deemed as successful if the successful localization probability of the novel localization and hookwire is different, addition the successful localization probability of the novel localization has statistic significantly higher than the successful localization probability of hookwire (p < 0.05).

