# 11.4 Significance Level and Power of the Trial

Significance level: 0.05; power: 0.8.

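### The primary superiority test is assigned to the Safety Analysis Set, so randomised patients with no device used or no safety record leave its denominator

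*Protocol*

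**What the plan says.** Protocol section 11.1 defines three analysis sets and then says what two of them are for.

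- **FAS.** Its definition begins: "Refer to the ideal subject set which is as close as possible to the intention-to-treat (ITT) principle". Its only stated use is that "we will use the FAS to analysis baseline information".
- **SAS.** The section introduces it as the set for judging safety and tolerance. Its membership rule is: "The SAS shall include all subjects who have used this investigational medical device and have at least one safety record". It is nevertheless given the efficacy comparison: "the primary endpoint and secondary endpoint will use the SAS to analysis".
- **Per-Protocol Set.** It is defined but given no analysis.

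Other sections bear on the point. Section 11.2 sets the superiority hypothesis and the success criterion of p < 0.05. Section 11.3.3, on effectiveness, names no population. Section 11.6 leaves missing data unfilled and treats them as invalid. Section 11.7 rules out sensitivity analysis. Section 7.2 gives randomisation numbers to consented patients and has the allocation envelope opened when the localization procedure begins. Section 7.3 lists only the novel needle as the investigational product.

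**The concern.** In a superiority trial the protection of randomisation belongs to the groups as randomised. A set that depends on what happened after allocation no longer has that protection. Here the condition for entry (a device was used and a safety record exists) is close to the outcome itself, since a patient who never receives a localization device has not been localized.

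The trial is open-label (section 7.1). Once the envelope is opened the operator knows the arm, so a decision not to go ahead can differ between arms. Few failures are expected, about 15 with hookwire and 8 with the novel device at the planned enrolment, so moving a modest number of patients in or out of the denominator can matter.

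There are two further consequences. The baseline table (FAS) need not describe the patients compared (SAS). And if the investigational device means the novel needle alone, as section 7.3 suggests, the SAS wording leaves out the hookwire arm, and a comparison between arms within it is undefined.

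**Working it through.** **1. Inputs.** All are from section 11.2: success 89% with hookwire and 97% with the novel device, one-sided alpha 0.05, power 80%, 15% drop-out. The stated size is "getting control group with 116 and intervention group with 232", inflated to 136 and 273 (409 in all).

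**2. The plan's own figures.**
- Drop-out inflation is n/(1 − 0.15): 116/0.85 = 136.5 and 232/0.85 = 272.9, total 409.4. The stated 136, 273 and 409 agree within rounding.
- By exact enumeration of Fisher's test, 116/232 has 84.4% one-sided power and 81.3% two-sided power. The size is adequate on either basis, so the concern is not about sample size.
- Enrolment of 136/273 with nobody lost gives 89.5% one-sided power.

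**3. Who leaves the SAS.** Setting section 11.1 beside section 6.1:

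| Patient | In the SAS? | Counted as |
|---|---|---|
| Device placed and holds | Yes | Success |
| Device used; failed release, dislodgement or fracture | Yes | Failure |
| Envelope opened, no device used | No | Not counted |
| Device used, no safety record | No | Not counted |

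Only the last two rows are at issue.

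**4. Assumed illustration.** Expected failures at the planned rates are 136 × 0.11 = 14.96, about 15, with hookwire, and 265 × 0.03 = 7.95, about 8, among novel-device patients who had a device used. Assume 8 of 273 novel-device patients (8/273 = 2.9%) and no hookwire patients had no device used.

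| Set | Hookwire failures | Novel-device failures | Success | Fisher, one-sided | Fisher, two-sided | Chi-square, uncorrected |
|---|---|---|---|---|---|---|
| SAS | 15/136 | 8/265 | 89.0% vs 97.0% | 0.0016 | 0.0023 | 0.0011 |
| As randomised, the 8 as failures | 15/136 | 16/273 (8 + 8) | 89.0% vs 94.1% | 0.051 | 0.075 | 0.063 |

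All three tests are shown because section 11.2 sizes the trial on a one-sided Fisher test, while section 11.3.1 reserves Fisher for expected counts below 5 and gives no sidedness for categorical tests. Eight is the smallest number that removes significance on all three. With 7 (15/136 vs 15/273), one-sided Fisher gives 0.037.

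**5. Other assumed rates.** These use one-sided Fisher at 136/273, with 89% and 97% success among patients who had a device used. As-randomised success is the success rate × (1 − non-use rate).

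| Non-use, hookwire / novel | SAS power | As-randomised success | As-randomised power |
|---|---|---|---|
| 0% / 0% | 89.5% | 89.0% vs 97.0% | 89.5% |
| 2% / 2% | 89.5% | 87.2% vs 95.1% | 80.6% |
| 5% / 5% | 88.7% | 84.6% vs 92.2% | 69.1% |
| 0% / 5% | 89.8% | 89.0% vs 92.2% | 22.1% |
| 5% / 0% | 89.1% | 84.6% vs 97.0% | 99.4% |

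The last two rows show that the direction depends on which arm loses patients.

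**6. False-positive rate.** Let true as-randomised success be 89% in both arms, and let a share of the novel arm, all failures, fall outside the SAS. The nominal 5% one-sided test then rejects in 6.3%, 11.0%, 17.7% or 40.6% of trials for a share of 1%, 2%, 3% or 5%. As randomised it rejects in 3.6%. This is the one-arm-only case, chosen to show how sensitive the test can be, and is not a forecast.

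**The case against.** The strongest reply is that the excluded group may be very small or empty. The envelope is opened only as localization starts (section 7.2), and surgery follows at once (section 8.4), so little time passes between known allocation and device use. The 15% drop-out allowance is a planning maximum with no stated cause and is not evidence of unused devices. All of this stands. It limits the likely size but does not make the stated set the right one for a superiority test.

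A reader might infer more than the documents support:

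- **That every unsuccessful or stopped procedure disappears.** Section 6.1 counts release, dislodgement and fracture failures, and such patients have used a device. An attempt stopped after puncture is arguably device use too.
- **That patients are regrouped by the device received.** Section 11.1 says who enters the SAS. It does not say how they are grouped.
- **That the bias must favour the novel device.** Leaving out unlocalized patients raises an arm's own success rate, but the difference between arms can move either way.
- **That any handful of exclusions overturns the result.** If 2 hookwire and 10 novel-device patients are excluded, the as-randomised failures are 17/136 vs 18/273. Two-sided Fisher gives 0.059, but one-sided Fisher gives 0.036 and uncorrected chi-square, which section 11.3.1 points to (smallest expected count 11.6), gives 0.044. The trial would still succeed under its one-sided basis.

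It could also be said that a statistical analysis plan might settle the matter. But section 11.1 is an explicit assignment, not a gap, and section 11.8 allows methods outside the protocol only after ethics committee approval.

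**Conclusion.** The point holds as a wrong choice of primary analysis set, with an effect of undetermined size. The protocol assigns its superiority test to a set conditioned on events after randomisation, leaves its near-intention-to-treat set without an efficacy role, and plans no analysis that would reveal the difference. The two sets give the same answer only if every randomised patient has a device used and a safety record.

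The documents give no rate of non-use, so every number beyond the plan's own sample size rests on assumed rates and on counting unlocalized patients as failures. Under those assumptions, exclusion of about 3% of the novel arm alone is enough to move the result from clearly significant to non-significant, whereas losses shared by both arms do less to the comparison. It should be corrected before analysis because the change is only to wording and the results are meant to support device registration (section 13.3).

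**What to change.** In section 11.1:

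- Make the FAS the primary set for localization success, defined as all patients whose allocation envelope was opened, analysed by assigned device.
- Count patients not localized as failures in the primary analysis. Other rules can be defended, for example for patients who stop for reasons unrelated to the device, but one must be fixed in advance and this one is conservative for each arm's success rate.
- Report the SAS result for localization success as supportive, and amend section 11.7 to allow it.
- Reword the SAS to cover users of either device, and keep it for complications and adverse events.
- Analyse pain and procedure time by assigned device among patients who had a procedure, since these values do not exist for the others.

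The cost is wording only, with the ethics committee review that section 13.4 requires for a material amendment. The planned 136 and 273 need not change on this account, though reported success rates may become slightly less favourable. As the table of assumed rates shows, 2% non-use in both arms would still leave 80.6% power as randomised.
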